#### 9.8 Termination of the Study

The study may be suspended or terminated early at the discretion of the Sponsor, for reasons such as incidence of unanticipated serious adverse device effects that may pose a risk to other subjects. In any early termination, already enrolled subjects will continue to be followed per the study protocol requirements.

Sponsor may also terminate a site prior to completion if it believes the site is no longer capable of participating (e.g., cannot fulfill subject enrollment or protocol compliance goals, site suspension by IRB/REB).

At termination of the investigation, each active site will undergo closeout monitoring to conclude any outstanding issues, resolve all data discrepancies and make sure any outstanding eCRFs are completed, discuss responsibilities with the Principal Investigator,

and discuss any other items relevant to the conclusion of the study. The termination process will be documented by a written report.

### 9.9 Device Log

#### 9.9.1 Device Log

The Research sites will use their commercially available STSF/ST catheters per the approved IFU and SURPOINT COA Protocol requirements. The site will keep a device log of the catheter used during the study.

The site Device Log will include the following information:

- Catalog number for catheters
- Serial/lot numbers
- Dates devices were used
- Subject IDs for whom devices were used
- Dates of return (as applicable)

Devices suspected of deficiency or device associated with a (device related or possibly related) adverse event should be returned immediately to BWI and will undergo thorough analysis. Returned devices must be decontaminated per hospital policy and labeled with the following:

- Subject identification number, or if unused, site number
- Complaint number
- Date of use/event or if applicable, specify "unused"
- Return type (device deficiency related, AE related, etc.)

All tracking information must be retained. Catheters must be returned to:

# 9.10 Electronic Case Report Forms

Electronic CRFs (eCRFs) have been developed to capture the information outlined in this Study Protocol. Data on these eCRFs will be monitored, corrected if necessary, and entered into a validated database. All changes made to the data will be tracked in the electronic audit trail, recording the current value, previous value, reason for change, date timestamp of data entry/change, and the name of the person who changed the data. The investigator will electronically sign all subject eCRFs as verification that the data have been reviewed and correctly reflects source documentation. Data from these eCRFs will be used to provide analysis of this study.

### 9.11 Source Documentation

Data entered into the eCRFs may be taken from source documentation, such as hospital procedure reports, admission and discharge summaries, and other hospital or physician office/clinic documents. If no standard hospital or office document exists to capture some of the information that may be unique to this study, a worksheet may be developed to record this information. Data collection instruments should clearly identify the individual collecting the data and the date of collection. The instrument of original capture of all study data will serve as the source document for future verification of for those data parameters. Privacy regulations will be observed during the use of these source documents during monitoring.

### 9.12 Subject Confidentiality/Record

All representatives of the Sponsor have undergone training for Privacy regulations and appropriate conduct for their compliance. For the duration of this study, all representatives of the Sponsor will comply with all privacy regulations regarding contact with subjects, their medical record information, copying of information, protection of the subject identities, and other aspects. Authorization for limited access to Protected Health Information by Sponsor personnel will be obtained as part of subject informed consent.

Site personnel should also be attentive to privacy considerations and should not transmit PHI outside of PI control (e.g., via .pdf or FAX) without redaction of patient identifiers.

Privacy considerations such as above will also be covered in protocol training for both Sponsor representatives and study site personnel.

#### 9.13 Data Management

The Sponsor will be responsible for all data management activities. These activities include development of a database, utilizing validated database software, into which all study data will be entered by the clinical sites. The Sponsor will be responsible for ensuring the overall integrity of the database.

# **APPENDIX A: STUDY DEFINITIONS**

Term	Definition
Adverse Event (AE)	Any unfavorable and unintended sign, medical occurrence, disease or injury (including abnormal laboratory findings) in subjects, users or other persons temporally associated with the use of a medicinal product or device whether or not related to the sponor's product.
	This definition includes events related to the medical device and/or the comparator, and events related to the procedure in which the device was used.
Adverse Device Effects (ADE's)	Adverse events related to the use of the medical device. This definition includes adverse events resulting from insufficient or inadequate instructions for use deployment, implantation, installation, or operation, or any malfunction of the medical device. This definition includes any event resulting from use errors or from intentional misuse of the investigation medical device.
AF/AT/AFL Episode	An episode of $AF/AT/AFL \ge 30$ seconds in duration.
AF Episode	An atrial fibrillation episode is defined as AF which is documented by ECG monitoring and has a duration of at least 30 seconds, or if less than 30 seconds, is present continuously throughout the ECG monitoring tracing. The presence of subsequent episodes of AF requires that sinus rhythm be documented by ECG monitoring between AF episodes
Anticipated AE	An effect which by its nature, incidence, severity or outcome has been identified as possible complications associated with the medical device and/ or intervention procedure.

Term	Definition
Atypical Flutter	Macroreentrant circuits within the atria where activation rotates around large obstacles that does not meet the criteria for Typical Flutter.
	Major (ISTH definition): Fatal bleeding AND/OR symptomatic bleeding in a critical area or organ, such as intracranial, intraspinal, intraocular, retroperitoneal, intraarticular, pericardial, or intramuscular with compartment syndrome AND/OR bleeding causing a fall in hemoglobin level of 2 g/dL (1.24 mmol/L) or more, or leading to transfusion of two or more units of blood.
Bleeding Complications (ISTH definition):	Clinically relevant nonmajor bleed (ISTH definition): An acute or subacute clinically overt bleed that does not meet the criteria for a major blrrd but ptomps a clinical response such that it leads to one of the following: hospital admission for bleeding; physician guided medical or surgical treatment for bleeding; change in antithrombotic therapy (including interruption or discontinuation).
	Minor bleeding (ISTH definition): All nonmajor bleeds. Minor bleeds are further divided into clinically relevant and not.
Catheter Insertion	Defined as the STSF/ST catheter breaching the sheath and entering the bloodstream.
Device Deficiency	Inadequacy of a medical device related to its identity, quality, durability, reliability, safety or performance, such as malfunction (failure of a medical device to perform in accordance with its intended purpose when used in accordance with the instructions for use or protocol), misuse or use error and inadequate labeling.
Documented AF/AT/AFL episode	An AF/AT/AFL episode documented by an electrocardiographic monitoring tool. This may include ILR, ECG, TTM, Holter monitor, or telemetry strip. Reporting of a symptomatic episode by a patient or in a referral letter is not considered a documented AF episode .
Paroxysmal AF	Paroxysmal AF is defined as recurrent AF ( $\geq 2$ episodes) that terminates spontaneously within 7 days. Episodes of AF of $\leq 48$ hours duration that are terminated with electrical or pharmacologic cardioversion should also be classified as paroxysmal AF episodes.
Permanent AF	Not appropriate in the context of patients undergoing catheter ablation of AF; refers to a group of patients where a decision has been made not to pursue restoration of sinus rhythm by any means, including catheter or surgical ablation.
Persistent AF (PsAF)	Persistent AF is defined as continuous AF that is sustained beyond 7 days and less than 1 year.

Term	Definition
Serious adverse event (SAE)	
 
Any adverse event that:         
 
Led to a death
 
Led to a serious deterioration in health that either:                 

Serious Adverse Device Effects (SADE's)	Adverse device effects that has resulted in any of the consequences characteristic of a serious adverse event.
Symptomatic AF/AT/AFL Episode	Symptom(s) which is/are exhibited by the subject which made them seek medical attention, and are concurrent with a documented episode of AF/AT/AFL by either ECG, TTM, Holter monitor, or telemetry recording. Symptoms may include but are not limited to: palpitations, irregular pulse (e.g., rapid, racing, pounding, fluttering, bradycardia), dizziness, weakness, chest discomfort, and breathlessness.
Typical Flutter	Atrial flutter is caused by a reentrant rhythm in either the right or left atrium. Typically initiated by a premature electrical impulse arising in the atria, atrial flutter is propagated due to differences in refractory periods of atrial tissue. This creates electrical activity that moves in a localized self- perpetuating loop. For each cycle around the loop, there results an electric impulse that propagates through the atria.
Unanticipated Serious Adverse Device Effect (USADE)	Serious adverse device effect which by its nature, incidence, severity or outcome has not been identified in the current version of the risk analysis report. NOTE: Anticipated SADE: an effect which by its nature, incidence, severity or outcome has been previously identified in the risk analysis report

Term	Definition
Ventricular Tachycardia (VT)	Ventricular tachycardia: a tachycardia (rate $\geq 100/\text{min}$ ) with three or more consecutive beats that originates from the ventricles independent of atrial or AV nodal conduction. Continuous VT for $\geq 30$ s or that requires an intervention for termination (such as cardioversion).

**SAP Version: 3.0** 

The following individuals have reviewed this version of the Statistical Analysis Plan and are in agreement with the content:

SAP Version	Revision Date (DD/MM/YYYY)	List of Changes
2.0	January 21, 2020  May 24, 2018	
 
Section 3, 8, 9.4, 9.4.1, 9.4.3, 9.4.6, 9.5: typos
 
Section 9.4.1: changed "predictive posterior probability" to "posterior probability"
 
Section 9.4.6: changed "Interaction terms will be examined" to "Interaction terms may be examined"
 
Study Name: added "and the THERMOCOOL SMARTTOUCH®" to the study name
 
Section 1, 2, 8: added 50 subjects using ST catheter with EPU as the study subjects and changed the number of study sites to be 45.
 
Section 5.1.2: added ", except atrio-esophageal fistula and PV stenosis 49,50, which may also be considered as primary adverse events if occurring
 

- greater than 7 days post the ablation procedure" to the primary safety endpoint definition
- Section 5.2.2: added 12-Month PAE Rate as secondary endpoint
- Section 9.4 Analyses of Primary Endpints: added anlaysis population for the primary effectiveness and safety endpoint in section 9.4.
- Section 9.4.1Final Analysis: added "Note that the final analysis will be performed if early success is not declared at either of the two interim looks. If early success is declared at either of the two interim looks, a summary of the primary endpoints based on full 12-month follow-up will be provided."
- Section 9.4.2 Interim Analyses:
  - Added "For the safety endpoint, among patients with full 12-month follow-up at the time of the interim analyses, any atrioesophageal fistula and PV stenosis occurring post procedure will be deemed PAE."
  - Specified the timing of interim analysis as "once subjects who are treated using STSF catheter with EPU who have completed 3-month (6-month) follow-up" and the interim analysis will be based on the data collected among subjects who are treated with STSF catheter only.
- Section 9.4.5 Subgroup Analyses:
  - Added 95% confidence interval and Fisher's Exact
  - Added Fisher-Freeman-Halton Exact Test when number of subgroup is greater than
     2
  - Removed gender and site from the subgroup analysis
  - Changed the cut points of operator's ablation procedure experience level to 75

left atrial ablation procedures for atrial
fibrillation in the past 12 months

 
Changed the cut point of contact force to
 

be <=10, 11-15, 16-20 and >20 grams
• Section 9.4.5.1 Poolability by Gender Analysis:
sdded sex-specific 90% confidence intervals of
the primary endpoints
• Removed the term "Evaluable Subjects" from the
SAP

#### **List of Abbreviations**

AAD antiarrhythmic drug

AF atrial fibrillation

AFL atrial flutter

AT atrial tachycardia

EPU external processing unit

ISTH International Society on Thrombosis and Haemostasis

PAE primary adverse event

PP per-protocol

PV pulmonary vein

PVI pulmonary vein isolation

QOL quality of life

RF radiofrequency

SAE serious adverse event

SF-12 12-Item Short Form Survey

SP Safety Population

ST THERMOCOOL SMARTTOUCH® catheter

STSF THERMOCOOL SMARTTOUCH® SF catheter

UADE unanticipated adverse device effect

#### 1. STUDY DESIGN

The SURPOINT COA study is a prospective, multicenter, non-randomized clinical evaluation of the VISITAG SURPOINT Module with EPU when used with the THERMOCOOL SMARTTOUCH® SF catheter (STSF) catheters or the THERMOCOOL SMARTTOUCH® (ST) catheter in treating subjects with symptomatic paroxysmal atrial fibrillation (PAF) who have failed at least one antiarrhythmia drug. A maximum of 330 subjects will be enrolled across up to 45 sites. Two hundred eighty (280) subjects will be treated using the STSF catheter with EPU and 50 subjects will be treated using the ST catheter with EPU. A few sites will be selected to enroll subjects to be treated only with the ST catheter. The remaining sites will enroll subjects to be treated with the STSF catheter. Two interim analyses are planned to take place after all subjects who are treated using the STSF catheter with EPU have completed their 3-month and 6-month follow-up visits for the evaluation of early success. The planned interim analysis will be based on data collected only in the subjects who are treated using STSF catheter with EPU. The final analysis of the primary effectiveness and safety endpoints will be based on all subjects's full 12-month follow-up data. Effectiveness and safety endpoints defined in association with the primary study objectives will be compared to the predetermined performance goals.

Enrolled subjects who satisfy all eligibility criteria will undergo the ablation procedure with the catheters and VISITAG SURPOINT Module. After the study ablation procedure, subjects will enter a 3-Month blanking period (Day 0-90). After the blanking period, subjects will enter the evaluation period (Days 91-365). Subjects having AF recurrence and/or receiving therapeutic interventions during the evaluation period will be considered effectiveness failures.

All subjects will undergo follow up visits at defined intervals (refer to Table 5-1 Schedule of Treatments and Evaluations in protocol). Subjects complete the SURPOINT COA study after the 12-month follow up visit.

#### 2. TREATMENT ASSIGNMENT

This is a single-arm study. The only treatment assigned is the THERMOCOOL SMARTTOUCH® SF (STSF) catheter and the THERMOCOOL SMARTTOUCH® (ST) catheter using VISITAG SURPOINTTM Module with External Processing Unit (EPU).

#### 3. RANDOMIZATION AND BLINDING PROCEDURES

This study is a non-randomized single-arm study. An independent group will perform the Bayesian interim analyses. The sponsor is not blinded to individual or aggregated data.

#### 4. INTERVAL WINDOWS

The required schedule for subject treatments and evaluations is summarized in Table 5-1 of the study protocol.

#### 5. PRIMARY AND SECONDARY ENDPOINT(S) AND ASSOCIATED HYPOTHESES

#### 5.1 Primary Endpoints and Associated Hypotheses

#### 5.1.1 Primary Effectiveness Endpoint

The primary effectiveness endpoint of this study is the effectiveness success rate at Month 12, defined as the proportion of subjects who are freedom from documented (symptomatic and asymptomatic) atrial fibrillation, atrial flutter and atrial tachycardia (AF/AFL/AT) (hereinafter collectively referred to as "atrial tachyarrhythmias") recurrence (episodes  $\geq$  30 secs on TTM or continuously recorded on the standard 12-leads ECG or holter) during the evaluation period (Day 91-365) and freedom from the following failure modes:

- Acute procedural failure, including:
  - Failure to confirm entrance block in all pulmonary veins at the end of procedure
- Repeat ablation failure, including:
  - > 1 repeat ablation procedures during the 3-Month Blanking Period (Day 0-90) after the index ablation procedure.
  - o Any repeat ablation procedure during the evaluation period.
- DC cardioversion for AF/AFL/AT following the 3-month blanking period
- Surgical treatment for AF/AFL/AT after the index ablation procedure.
- AAD failure: Taking a new AAD for AF, a previously failed AAD at a greater than the highest ineffective historical dose during the evaluation period.

This study is designed to compare the primary effectiveness of the VISITAG SURPOINT Module with EPU to a pre-determined performance goal of 50%, which is indicated as the minimum acceptable success rate at 12 months for a paroxysmal AF population in the 2017 HRS/EHRA/ECAS/APHRS/SOLAECE consensus statement.

The final analyses for primary effectiveness endpoint will apply Bayesian methods and use a beta-binomial model .

The hypotheses to be tested for this evaluation are:

$$H_0: p \le 0.50$$
 vs.  $H_A: p > 0.50$ ,

where p is the effectiveness success rate

#### **5.1.2** Primary Safety Endpoint

The primary safety endpoint is the proportion of subjects with any primary adverse event (PAE) occurring within 7 days following an AF ablation procedure (including the initial and repeat procedures) using the STSF/ST catheter with EPU, except atrio-esophageal fistula and PV stenosis , which may also be considered as primary adverse events if occurring greater than 7 days post the ablation procedure. The PAE rate will be compared against the performance goal of 14%.

The final analyses for primary safety endpoint will apply Bayesian methods and use a beta-binomial model .

The hypotheses to be tested for this evaluation are:

$$H_0: q \ge 0.14$$
 vs.  $H_A: q < 0.14$ 

where q is the PAE rate.

#### 5.2 Secondary Endpoints

No formal statistical hypothesis and inferential statistics will be formulated and performed for the secondary endpoints.

#### **5.2.1** Secondary Effectiveness Endpoints

- Acute Procedural Success
  - o % of subjects with ipsilateral PVI (entrance block) at the end of the procedure
  - o % of subjects with ipsilateral PVI (entrance block) after first encirclement (evaluated prior to the 30-minute waiting period and adenosine challenge)
  - o % of touch-up (ablation of acute reconnection) among all targeted veins
  - o Anatomical location of acute PV reconnection after first encirclement
- Repeat ablation procedures during 12-month period post-procedure
  - o Incidence (%) of repeat ablation procedures
  - o % PVs re-isolated among all of the targeted PVs at repeat procedure

 % repeat ablation procedures requiring new linear lesions and/or identifying new foci outside of initially isolated area among the repeat ablation procedures

#### • 12-Month Single Procedure Success

o The 12-month single procedure success is defined as freedom from documented AF/AFL/AT recurrence (episodes ≥ 30 secs) during the Evaluation Period after a single ablation procedure and off AADs. Any repeat ablation procedure or AAD therapy will be deemed effectiveness failure for this analysis.

#### 5.2.2 Secondary Safety Endpoints

#### • 12-Month PAE Rate:

12-Month PAE Rate is the cumulative incidence of primary adverse events occurring within seven (7) days following an AF ablation procedure using study catheters with EPU and any late onset atrio-esophageal fistula or PV stenosis through 12 months

- Incidence of Unanticipated Adverse Device Effects (UADEs)
- Incidence of Serious Adverse Events (SAEs) within 7 days (early onset), >7 to 30 days (peri-procedural) and >30 days (late onset) of initial ablation
- Incidence of bleeding complication (ISTH definitions): a) major bleeding, b) clinically relevant non-major and c) minor bleeding

#### 5.3 Additional Endpoints

No formal statistical hypothesis and inferential statistics will be formulated and performed for the additional endpoints.

#### • Procedural Data:

- Total procedure time, PVI time, RF application time, mapping time and RF application time per lesion
- Total Fluoroscopy Time
- Fluid delivered from the study catheter
- o Location of RF applications, number of RF applications
- o RF Ablation parameters per application (e.g. temp, power, impedance, CF etc.)
- Device(s) utilized (per ablation)
- VISITAGTM Settings

- o CF range
- Power range
- Tag Index Assessment per anatomical region
- Quality of Life (QOL): SF-12

#### 5.4 Health Economic Data

The primary health economic data will include the cost and frequency of hospitalization for the study index ablation procedure, as well as any additional hospitalizations during the study period. The health care utilization during hospitalizations will be assessed by utilizing all data available for this study such as copies of the subject's hospital bills (UB04) and/or itemized hospital bills.

The health economic data associated with follow up care will include any repeat ablation procedure for treating arrhythmia, any inpatient or outpatient visit (including ER admissions) to address post-procedural complications or any procedure related condition and any inpatient or outpatient visit (including ER admissions) related to arrhythmia and cardiovascular conditions.

#### 6. LEVEL OF SIGNIFICANCE

The type I error for the interim and final analyses of the primary endpoints is controlled at one-sided 5%.

#### 7. ANALYSIS SETS

For the analysis of study endpoints, the analysis populations defined in the following will be used:

- Safety Population: The SP will consist of all enrolled subjects who have undergone insertion of the STSF/ST catheter and use of the VISITAG SURPOINTTM Module with EPU. The safety population (SP) will be used to analyze safety endpoints.
- Per Protocol (PP) Population: The PP population will include subjects who satisfy the following criteria. The PP population will be used for the analysis of effectiveness endpoints.
  - o are enrolled and meet all eligibility criteria
  - have undergone RF ablation
  - o are treated with the STSF/ST catheters with the VISITAG SURPOINT™ Module with EPU, and have been treated for the study-related arrhythmia

- Full Set Effectiveness Population: This population will include those who have met the following criteria. The full set effectiveness population will be used to analyze the effectiveness endpoints.
  - o are enrolled
  - o have undergone RF ablation
  - o are treated with the STSF/ST catheters with the VISITAG SURPOINT™ Module with EPU, and have been treated for the study-related arrhythmia

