Cardiac perforation may result from catheter manipulation or application of RF. Published risks of cardiac perforation range from <1% to 2.5%. This potentially life-threatening injury may result in cardiac tamponade and may require percutaneous pericardial drainage or surgical repair. In the SMART-AF study using the THERMOCOOL SMARTTOUCH® Catheter with contact force sensing technology, there were 4 (2.48%, 4/161) reported incidents of tamponade. Additionally, in the SMART-SF study using a new investigational catheter with contact force sensing technology the observed incidence of tamponade was 1.3% (2/159). Significant hemodynamic compromise can result in neurologic injury or death. An increased risk of cardiac perforation during ablation may be associated with the use of saline-irrigated electrode catheter due to its ability to create a larger, deeper lesion. This risk is greatest in a thin walled chamber (i.e., right or left atria or right ventricle). However, the risk of perforation related to a deep steam pop is reduced if RF energy is not delivered perpendicular to the wall at power above 35 or 40 watts. If the lesion is deeper the risk of steam pop is higher above 35-40 watts.

Injury to a cardiac valve may result from catheter manipulation or the application of RF current (risk <1%). This may produce valvular insufficiency and possibly require surgical valve replacement.

The application of RF energy along the posterior left atrium can result in thermal injury to the esophagus and the formation of an atrio-esophageal fistula. This is a rare (0.04%) but severe complication of RF ablation requiring surgical intervention or that may result in permanent impairment. Reducing power at sites in close proximity to and/or avoiding sites directly over the esophagus may reduce the risk of thermal injury.

Injury to the phrenic nerve may occur as a result of RF application in the region of the right pulmonary veins. The reported incidence of phrenic nerve injury varies from 0% to 0.48% when RF energy is used for catheter ablation. Prior to ablation in the region of the right superior pulmonary vein, precautionary measures such as pacing maneuvers are recommended to evaluate proximity to the phrenic nerve.

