#### **3.2 Subject Disposition**

- Enrolled Subjects: subjects who sign the informed consent.
- Excluded Subjects: subjects who do not have the STSF/ST catheter inserted or have the STSF/ST catheter inserted but do not undergo ablation with VISITAG SURPOINTTM Module. Subjects who have the STSF/ST catheter inserted but do not undergo ablation with VISITAG SURPOINTTM Module will be followed for 12-months.
- Lost to Follow-up Subjects: subjects who are enrolled and have STSF/ST catheter inserted and undergo ablation with VISITAG SURPOINTTM Module, but contact is lost after most recent follow-up visit (despite 3 documented attempts).
- Withdrawn / Early Termination Subjects: subjects who withdraw consent for study participation or are withdrawn by the investigator or are terminated from the study prior to completion of all follow-up visits.
- **Completed Subjects:** enrolled subjects who completed the 12-month follow-up visit.

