## 7.7 Analysis Sets

For the analysis of study endpoints, the analysis populations defined in the following will be used:

- Safety Population: The SP will consist of all enrolled subjects who have undergone insertion of the STSF/ST catheters and use of the VISITAG SURPOINT™ Module with EPU. The safety population (SP) will be used to analyze safety endpoints.
- Per Protocol (PP) Population: The PP population will be used for the analysis of effectiveness endpoints. The PP population will include subjects who satisfy the following criteria:
  - are enrolled and meet all eligibility criteria
  - o have undergone RF ablation
  - are treated with the STSF/ST catheters with the VISITAG SURPOINT™ Module with EPU, and have been treated for the study-related arrhythmia
- Full Set Effectiveness Population: The full set effectiveness population will be used to analyze the effectiveness endpoints. This population will include those who have met the following criteria:
  - $\circ$  are enrolled
  - have undergone RF ablation
  - are treated with the STSF/ST catheters with the VISITAG SURPOINT™ Module with EPU, and have been treated for the study-related arrhythmia

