#### 9.2 Subject Disposition

Disposition of the study subjects are defined as the following.

- Enrolled Subjects: subjects who sign the informed consent.
- Excluded Subjects: subjects who do not have the STSF/ST catheter inserted or have the STSF/ST catheter inserted but do not undergo ablation with VISITAG SURPOINTTM Module. Subjects who have the STSF/ST catheter inserted but do not

undergo ablation with VISITAG SURPOINTTM Module will be followed for 12 months.

- Lost to Follow-up Subjects: subjects who are enrolled and have STSF/ST catheter inserted and undergo ablation with VISITAG SURPOINTTM Module, but contact is lost after most recent follow-up visit (despite 3 documented attempts).
- Withdrawn / Early Termination Subjects: subjects who withdraw consent for study participation or are withdrawn by the investigator or are terminated from the study prior to completion of all follow-up visits.
- Completed Subjects: enrolled subjects who completed the 12-month follow-up visit.

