#### 9.4 Analysis of Primary Endpoints

The primary effictiveness endpoint is the proportion of patients that are free from primary effectiveness failure at Month 12. The failure modes are defined in the section 5.1.1. The effectiveness success rate at Month 12 will be compared against the performance goal of 50%. The final analyses will apply the Bayesian methods using a beta-binomial model. The analysis population for the primary effectiveness endpoint will be the per protocol (PP) population.

The primary safety endpoint is the proportion of patients that had Primary Adverse Event (PAE) within 7 days (PV stenosis and atrio-esophageal fistula may occur up to 3 months). The PAE rate will be compared against the performance goal of 14%. The final analyses will apply the Bayesian methods using a beta-binomial model. The analysis population for the primary safety endpoint will be the safety population.

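### The Safety Population turns on an undefined 'use' of the SURPOINT module, so a complication that stops the case after catheter insertion may be left out of the primary safety rate

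*SAP*

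**What the plan says.** SAP 7 defines the Safety Population thus: "The SP will consist of all enrolled subjects who have undergone insertion of the STSF/ST catheter and use of the VISITAG" SURPOINT module with EPU. Protocol 7.7 has the same two-part rule: "undergone insertion of the STSF/ST catheters and use of the VISITAG" SURPOINT module with EPU. Neither document says what counts as use.

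This set supplies the primary safety test. SAP 9.4 states: "The analysis population for the primary safety endpoint will be the safety population". SAP 9.4.1 takes n as the size of that population and y as the number of subjects with a PAE.

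The disposition sections deal with a group that sits on the edge of this rule. SAP 9.2 classes as Excluded "subjects who do not have the STSF/ST catheter inserted or have the STSF/ST catheter inserted but do not undergo ablation with VISITAG" SURPOINT. Protocol 3.2 uses the same label and then adds that "Subjects who have the STSF/ST catheter inserted but do not undergo ablation with VISITAG" SURPOINT "Module will be followed for 12-months". The plan therefore foresees these subjects and collects their data.

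The endpoint text points the same way as the population. Protocol 4.1.2, 6.2.1 and 7.5.1.2 and SAP 5.1.2 all tie PAEs to an AF ablation procedure performed with the study catheter and the EPU or module.

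On mechanism, the risk analysis in Protocol 1.3.1 says: "Cardiac perforation may result from catheter manipulation or application of RF".

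**The concern.** A subject can have the study catheter inserted, suffer a complication from manipulating it, and have the case stopped before any module-guided ablation. If no ablation means no use of the module, that subject leaves both parts of the primary safety rate. The exclusion then depends on the outcome, because the complication is what kept the subject out. Such an exclusion removes events more readily than uneventful cases, so it lowers the rate, which is the favourable direction against a 14% upper goal.

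No other planned analysis picks these subjects up. The secondary safety endpoints (SAP 9.5), the exact binomial check (SAP 9.4.4.1) and the safety tipping-point analysis (SAP 9.4.4.6) all use the same Safety Population. This is a single-arm study whose sponsor is not blinded (SAP 3), so an undefined membership rule also leaves room for case-by-case decisions after outcomes are known.

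**Working it through.** **Inputs.** Goal 14%, prior Beta(1,1), success if Pr(q < 0.14 | y, n) > 0.95, no imputation for safety (SAP 9.4.1). Planned PAE rate 8%, 330 enrolled, 10-15% attrition, about 30 lost before treatment (SAP 8). The number k of subjects with the catheter inserted, no module ablation and a PAE is not in the documents; I assume k = 0 to 3.

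**Rule.** The posterior is Beta(1 + y, 1 + n − y). The pass limit is the largest y whose posterior probability below 0.14 exceeds 0.95. All figures are for the fixed-sample final analysis; the interim looks were not simulated.

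**The plan's own figure.** SAP 8 claims more than 90% power at 8%. Power is P(Y ≤ limit | n, 0.08):

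| n | Source | Limit | Power at 8% | Pass at 14% |
|---|---|---|---|---|
| 300 | 330 − 30 | 31 | 94.0% | 3.6% |
| 297 | 330 × 0.90 | 31 | 94.6% | 4.2% |
| 281 | 330 × 0.85, rounded up | 29 | 93.4% | 4.1% |

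The claim is reproduced. The question is who is counted, not the power figure.

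**Effect near the limit.** The limit is 31 for every n from 295 to 300. Adding back subjects who each had a PAE:

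| Analysed | Posterior | With events added | Posterior |
|---|---|---|---|
| 31/297 (10.4%) | 0.960, pass | 32/298 (10.7%) | 0.944, fail |
| 31/300 (10.3%) | 0.965, pass | 32/301 (10.6%) | 0.9515, pass |
| 31/300 (10.3%) | 0.965, pass | 33/302 (10.9%) | 0.934, fail |

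One or two omitted events decide the result there. Each moves the rate by about 0.3 percentage points (10.7 − 10.4).

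**Effect at the planned rate.** 24/300 (8.0%) has posterior 0.999. Adding three events gives 27/303 (8.9%), posterior 0.996. Adding six gives 30/306 (9.8%), posterior 0.983. Both pass.

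**Type I error.** Let the true rate be 14% among 300 inserted subjects, and let k of those with a PAE be dropped. The analysed n is 300 − k, for which the limit is still 31 when k is 0 to 3. The trial passes on safety if the full count Y is at most 31 + k, so the chance is P(Y ≤ 31 + k | 300, 0.14):

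| k | Condition | Chance of passing |
|---|---|---|
| 0 | Y ≤ 31 | 3.6% |
| 1 | Y ≤ 32 | 5.3% |
| 2 | Y ≤ 33 | 7.5% |
| 3 | Y ≤ 34 | 10.4% |

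A second way is to fix the remaining rate at (42 − k)/(300 − k), where 42 = 0.14 × 300. It gives 5.1%, 7.1% and 9.6% for k = 1, 2, 3. Both exceed 5% from k = 1.

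These figures assume that every dropped subject had a PAE. Uneventful subjects dropped for other reasons, such as an equipment fault, would pull the other way.

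**The case against.** A reader might infer that these subjects certainly drop out. The documents do not go that far. The Safety Population asks for use of the module, whereas the Per Protocol and Full Set populations in the same sections ask that RF ablation was performed and the subject treated with the module. The different wording may mean that the Safety Population is broader. Protocol 1.8.2 says the EPU runs automatically once the module is installed and activated, so a subject whose case stopped before ablation could be said to have used it. The Excluded label is a disposition term, and no sentence links it to Safety Population membership. This objection stands in part: it turns a definite omission into a possible one. It does not remove the problem, since a primary analysis set should not rest on an undefined word.

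A reader might also infer that the events are lost. They are not. Adverse events are collected from consent (Protocol 6.1), primary and cardiac serious events go to the Clinical Events Committee (6.13), and serious events are summarised to the FDA (8.5.5). Only the formal rate could miss them.

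Two more points have weight. First, the study evaluates the module with catheters that are already approved, so an exposure-based set has some logic. That supports keeping it as a secondary view, but not leaving inserted subjects without any planned safety analysis. Second, the sequence in Protocol 5.4 puts transseptal puncture and the left atrial map before introduction of the study catheter. A complication at those steps is left out by the insertion condition, not by the module condition.

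**Conclusion.** The concern holds as a gap in definition. Subjects with the catheter inserted but no module ablation may be left out of the primary PAE rate, and no planned analysis reports their safety. Where a complication after insertion is the reason for their exclusion, the bias is downward.

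The size is small and conditional. With an assumed 0 to 3 such subjects, the verdict can change only near 31 events in about 300. At the planned 8% rate it does not change. If the true rate equals the 14% goal, one such omission already takes the chance of passing on safety to about 5.3%, above the level that SAP 6 and 9.4.1 say is controlled, and three take it to about 10.4%.

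A reader might conclude that the safety result is unreliable or that the stated power is wrong. Neither follows: the power figure is reproduced, and the number of affected subjects may be zero. The change should be made because it concerns a primary endpoint and costs little.

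**What to change.** 1. In SAP 7 and Protocol 7.7, define the Safety Population as all enrolled subjects with the STSF/ST catheter inserted, whether or not module-guided ablation was delivered. Protocol Appendix A already defines catheter insertion.
2. Align the primary safety endpoint in Protocol 4.1.2, 6.2.1 and 7.5.1.2 and in SAP 5.1.2, so that PAEs within the stated windows after an attempted procedure with catheter insertion are counted. Changing the population alone would add subjects whose events the endpoint text might still not count.
3. Add the module-used subset to SAP 9.4.4 as a sensitivity analysis, with a definition of use.
4. State in SAP 9.2 and Protocol 3.2 that the Excluded label does not decide Safety Population membership.

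The cost is wording; these subjects are already followed for 12 months. The PAE rate may be slightly less favourable. Events before study-catheter insertion, for example at transseptal puncture, remain outside the set, and the report should say so.
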